**Aim 2**

The spoken discourse measure data will be used in a canonical discriminant function analysis (DFA) to identify the optimal discourse classification functions that separate groups. DFA is a multivariate procedure that is used to predict group membership. In our

case, where there are > 2 diagnostic groups, Wilks' lambda values, in a stepwise approach, will be used to identify the final set of variables that account for the maximal variance for group differences. This step will eliminate variables that do not contribute significantly to group variance. Redundant variables will also be deleted. The DFA approach will yield multiple potential models that will be evaluated for classification accuracy using sensitivity and specificity analyses. Receiver operating characteristic curves will be used to evaluate discriminant function accuracies as discrimination thresholds vary.

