**1.0 Purpose of the study:**

**Aim 1 will characterize PD-MCI (Parkinson's disease mild cognitive impairment), PDN (Parkinson's disease without cognitive impairment), and HA (healthy adult) spoken discourse, cognitive, and motor speech profiles.** Phase 2 biomarker development requires robustly characterized cohorts in which to test candidate biomarkers. Using a standardized battery of cognitive, language, and motor speech tests PD participants will be assigned to PD-MCI (single/multi-domain) or PDN groups. We propose collecting spoken discourse samples using standardized elicitation protocols. The same tasks will be extracted from the extant HA database. Researchers will transcribe, code, and analyze discourse samples. Group differences (including sub-analyses for single and multi-domain MCI subtypes), elicitation stimuli effects, and group x stimuli interactions will be examined using multivariate and mixed-design ANOVA procedures.

**Aim 2 will develop and evaluate the classification accuracy of an optimally weighted discourse classification function for PD-MCI and PDN.** We propose using discriminant function analysis to identify an optimized composite variable that best predicts PD-MCI, PDN, and HA group membership. Sensitivity/specificity analyses, positive/negative predictive values, and receiver operating characteristic curves will be used to evaluate the discourse classification function properties.

The **primary endpoint** is an optimally weighted discourse function that can classify PD-MCI with > 80% sensitivity/specificity.

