**2.0 Background / Literature Review / Rationale for the study:**

Individuals with Parkinson's disease (PD) have a 6-fold increased risk of dementia. PD mild cognitive impairment (PD-MCI) is thought to be a transitional state to dementia for

many of those affected. **Difficulties monitoring early cognitive impairments, and concomitant delays in treatment initiation, are major barriers** to the accurate diagnosis of and the development of interventions for cognitive impairments in PD. A biomarker is any characteristic that can be objectively measured and indicates normal/pathogenic processes or responses to therapeutic interventions. Biomarkers can be genetic markers, neural markers, and observable behaviors. In the absence of neuropsychological findings, early dementia can still be detected in spoken discourse. Thus, a **spoken discourse biomarker** can be a valuable supplement to extant neuropsychological evaluation for **monitoring cognitive-linguistic changes in real world environments**. The **long-term objective** of this research is to improve the early and accurate diagnosis of PD cognitive impairment with a reliable spoken discourse biomarker. Research shows that discourse features including grammar errors, information content/efficiency, coherence, and verbal disfluencies hold promise for detecting PD cognitive impairments. Additionally, our pilot suggests that an optimally weighted composite variable, and no one single variable, is best able to discriminate PD spoken discourse. A **major barrier** is the absence of a spoken discourse biomarker that has been rigorously developed and tested on a meticulously-characterized cohort of PD-MCI, PD without cognitive impairment (PDN), and healthy adults (HA). Using the Fit-for-Purpose framework, **the goal of the proposed research is to complete a Phase 2 spoken discourse biomarker study**. The **overarching hypothesis** is that PD-MCI and PDN will have unique profiles of spoken discourse impairments that are distinguishable from each other and from HA.

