## **4.0 Sample Size:**

We will enroll 86 PD participants (43 individuals with PD and normal cognition and 43 individuals with PD mild cognitive impairment). Data from 43 age/education/sex matched HA will be sampled from an extant repository.

Sample sizes for ANOVA and DFA were calculated using G\*Power. For Aim 1, a sample of 129 participants for MANOVA procedures with 3 IVs (PD-MCI, PDN, HA), 15 dependent variables (6 canonical variables), and up to 3 covariates will detect a minimum of  $f^2$  of 0.16 (medium-sized effects) with power of 0.90, and  $\alpha=0.05$ . The available effect size estimates for the 8 candidate discourse variables range from  $f^2$  of 0.33 to 0.50 (medium to large effects). With the smallest anticipated effect size based on our pilot data ( $f^2 = .33$ ) 129 participants in a mixed ANOVA with 2 IVs (Group [3 levels]) and Task [2 levels]) with up to 2 covariates will yield power of 0.86,  $\alpha=0.05$ . At the highest estimated effect size ( $f^2 = .50$ ), the same sample size will yield power of 0.99,  $\alpha=0.05$ . For **Aim 2**, DFA procedures with 3 groups and 8 discourse variables with 129

participants will detect  $f^2$  of .10 (small-medium effects) with power of 0.90,  $\alpha=0.05$  and power of 0.85, if  $\alpha=0.025$ . For the sensitivity and specificity analyses a sample of 129 participants will detect sensitivity and specificity values of 0.83 or higher with a 90% confidence interval precision of 0.10, given an expected disease (PD-MCI) prevalence of 30%, a conservative prevalence estimate. This precision level is consistent with guidelines for Phase 2 studies.

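### Aim 2 plans no internal validation of the stepwise discriminant function, so the accuracy compared with the >80% primary endpoint is apparent accuracy, biased upward by about 1 to 5 points for the planned three-group analysis

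*Combined protocol and SAP*

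**What the plan says.** Section 1.0 makes an accuracy figure the primary endpoint: "an optimally weighted discourse function that can classify PD-MCI with > 80% sensitivity/specificity". Its Aim 2 paragraph describes the product as an "optimized composite variable that best predicts PD-MCI, PDN, and HA group membership".

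Section 8.0 (Proposed Data Analysis, Aim 2) builds that function from the study data. Wilks' lambda values, "in a stepwise approach, will be used to identify the final set of variables". Redundant variables are dropped, and then: "The DFA approach will yield multiple potential models that will be evaluated for classification accuracy using sensitivity and specificity analyses". ROC curves follow, with the threshold left to vary.

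Section 4.0 covers both steps with one sample of 43 PD-MCI, 43 PDN and 43 HA. The discriminant analysis is sized as "DFA procedures with 3 groups and 8 discourse variables with 129" participants, and the accuracy analysis begins: "For the sensitivity and specificity analyses a sample of 129 participants". It also gives anticipated effects: "The available effect size estimates for the 8 candidate discourse variables range from" f² 0.33 to 0.50.

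The available text mentions no split sample, cross-validation, bootstrap, external sample or optimism correction. The double-scoring and reliability checks in sections 13.0 and 16.0 concern test scoring and data forms. A variable-selection rule is given, but no rule for choosing among the resulting models. Section 1.0 does not say whether specificity is measured against PDN alone or against PDN plus HA.

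**The concern.** A rule whose variables and weights were chosen on a data set is, on average, more accurate there than in new patients. Here that in-sample figure is the primary endpoint and has a fixed pass mark. If true accuracy is slightly under 80%, the study could report the endpoint as met by a function that would not meet it in new patients. A confidence interval around the in-sample value does not reveal this, because the interval is centred on the inflated figure. Section 2.0 names as the gap to be filled the "absence of a spoken discourse biomarker that has been rigorously developed and tested on a meticulously-characterized cohort", so an honest accuracy estimate is central to the study's purpose.

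**Working it through.** **The plan's own figures reproduce.**
- Discriminant analysis power: MANOVA global test with df1 = 8 × 2 = 16, df2 = 240 and noncentrality 129 × 2 × 0.10 = 25.8. Power is 0.905 at α = 0.05 and 0.846 at α = 0.025 (plan: 0.90 and 0.85).
- Precision: 1.645² × 0.83 × 0.17 / 0.10² = 38.2 cases; 38.2 / 0.30 = 127 (plan: 129).

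Neither calculation allows for optimism. The sample size is not in question.

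**Inputs.** From section 4.0: 43 per group, 8 candidate variables, f² 0.33 to 0.50. Assumed, because the documents do not say: normal data, correlations between variables, the pattern of group means, stepwise entry and removal limits, equal priors, no cut-off tuning.

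**A case checkable by hand.** Let only PD-MCI be shifted, by δ SD on each variable. With three equal groups f² = δ² × (1/3)(2/3), so f² = 0.33 gives δ² = 0.33 × 4.5 = 1.485. With 8 variables correlated 0.3, D² = 8 × 1.485 / (1 + 7 × 0.3) = 3.83 and D = 1.96. A rule with known weights would have sensitivity and specificity Φ(D/2) = Φ(0.98) = 83.6%. Rules actually selected and fitted on 129 people had true values averaging 76.7/82.2%, but scored 81.4/85.0% on their own data.

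**Examples** (three-group function, specificity against PDN plus HA, correlation 0.3, 300 simulated studies each; optimism is for the average of sensitivity and specificity):

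| f², mean pattern | Apparent sens/spec, % | True sens/spec, % | Optimism, points | Both apparent >80% | Both true >80% |
|---|---|---|---|---|---|
| 0.33, linear | 72.2/83.4 | 65.7/81.0 | 4.4 | 8% | 0% |
| 0.33, PD-MCI only | 81.4/85.0 | 76.7/82.2 | 3.7 | 57% | 4% |
| 0.33, mixed | 87.1/93.5 | 82.6/90.8 | 3.6 | 93% | 84% |
| 0.50, mixed | 92.8/96.2 | 89.8/94.9 | 2.1 | 100% | 100% |

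Ten-fold cross-validation with selection repeated in each fold gave 82.7/91.2% and 89.5/94.5% for the last two rows, close to the true values.

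**Wider grid.** 27 scenarios, 1,500 runs each: all 8 variables informative at f² 0.33, 0.50 or spaced between; correlation 0, 0.3 or 0.5; PDN shifted by 0, 30 or 50% of the PD-MCI shift; entry at p = 0.05, removal at 0.10.

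| Function and comparison | Median optimism (range), points | If 0.33-0.50 is f, not f² |
|---|---|---|
| Three-group, PD-MCI v PDN plus HA | 3.4 (1.1-4.4) | 4.1 (2.5-6.0) |
| Three-group, PD-MCI v PDN | 3.5 (1.2-4.7) | 4.3 (2.6-6.6) |
| Two-group, PD-MCI v PDN | 4.6 (1.5-6.1) | 5.7 (3.9-7.9) |

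Repeats of the three-group grid gave upper ends between 4.2 and 4.9. With only 4 of the 8 variables informative, the three-group v rest range was 0.6-4.7. Choosing the cut-off on the same ROC curve raised the inflation to about 2.6-10.3 points, over a wider set of effect sizes.

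**Effect on the endpoint.** A false pass means both estimates exceed 80% but that function's true values do not both do so. With the lower true value at 0.72-0.80, the median false-pass rate was 46% (three groups v rest) and 42% (two groups), falling to 20% and 13% with nested cross-validation. A repeat gave 48% to 23% and 43% to 15%. With the lower true value at 0.86 or more, it was 0-2%.

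**The case against.** **Silence is not a commitment to in-sample scoring.** This is true, and the analyst might cross-validate anyway. But the plan does not require it, and leaving cases out only after the variables have been chosen keeps the selection bias.

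**This is Phase 2 development, and validation comes later.** That is fair as far as external validation goes, and none is asked for. But a pass mark is set now, and internal validation needs no further data.

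**The size rests on assumptions.** This stands. Correlations, mean patterns and entry limits are not in the documents. Omission and direction are secure; the number of points is indicative.

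**Sampling error is larger.** It is: with 43 PD-MCI the 90% half-width is 1.645 × √(0.83 × 0.17 / 43) = 9.4 points, and false passes near the threshold remain at 13-23% even with cross-validation. But the bias runs in one direction only.

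**The harm is confined to a band.** This also stands. In one repeat of the grid, only 7 of the 27 three-group scenarios had the lower true value between 0.72 and 0.80. False-pass rates also presume a point-estimate decision rule, which section 1.0 does not spell out.

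A reader might infer a bias of up to 6 points for the planned analysis at the plan's f². The documents do not support that. Section 4.0 and Aim 2 describe a three-group analysis, and in the grid at those f² values 6 points appears only for a two-group PD-MCI v PDN function. Section 1.0 does call the function one for PD-MCI and PDN, so a two-group version cannot be excluded, but it is not what the analysis section sets out.

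**Conclusion.** The concern holds as a cheap improvement. Followed as written, Aim 2 selects, weights and scores the function on the same 129 participants, so the accuracy compared with 80% is apparent accuracy. The expected inflation is about 1 to 5 points for the three-group function at f² 0.33 to 0.50, under the stated assumptions. It is larger if those values are f, if a two-group function is used, or if the cut-off is tuned on the same curve. The endpoint call is at risk mainly when the lower true value lies just below 80%.

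Two further inferences would go too far. The study is not shown to be likely to claim success wrongly: that depends on true accuracy, which the documents do not give, and several strong-effect scenarios pass on both apparent and true values. Nor is 0.83 a planned margin of 3 points over the threshold; it is an input to the precision calculation.

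**What to change.** Add to Aim 2:

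> Sensitivity and specificity for the primary endpoint will be estimated from the three-group discriminant function by repeated 10-fold cross-validation, with stepwise selection, redundancy deletion, choice among models and any cut-off choice repeated inside each training fold. The >80% endpoint will be assessed on these cross-validated estimates, reported with 90% intervals, for one pre-specified primary comparison [sponsor to name: PD-MCI v PDN, or PD-MCI v PDN plus HA]; the other comparison is secondary. In-sample values will be labelled apparent accuracy.

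If the intervals are bootstrapped, the whole procedure should be resampled with all copies of a participant kept in the same fold. When copies were split across folds, about 54-72% of the optimism returned.

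**Cost.** Wording and computing; no new participants. Reported accuracy will be less favourable, and cross-validation was itself slightly pessimistic (median 0.3-0.4 points, at most 1.2). The real price is more false failures: with the lower true value at 0.80-0.86, the median rate rises from 7% to 28% (three groups v rest) and from 5% to 26% (two groups). Averaged over the 27 scenarios, weighted equally, wrong calls in either direction still fall, from 22% to 15% and from 22% to 14%. That net gain depends on the grid chosen.

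### The primary endpoint sets an 80% pass mark but no deciding model, cut-off or comparison, so the plan permits a best-of-many result to be read as a single result

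*Combined protocol and SAP*

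**What the plan says.** Section 1.0 (Purpose of the study) says that the primary endpoint "is an optimally weighted discourse function that can classify PD-MCI with > 80% sensitivity/specificity". This is a numeric pass mark on two measures.

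Section 8.0, Proposed Data Analysis, Aim 2, describes the route to that function. Variables are chosen stepwise by Wilks' lambda and redundant ones are dropped, with no entry, removal or redundancy criterion given. The paragraph continues: "The DFA approach will yield multiple potential models that will be evaluated for classification accuracy using sensitivity and specificity analyses". It closes: "Receiver operating characteristic curves will be used to evaluate discriminant function accuracies as discrimination thresholds vary".

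Section 4.0 (Sample Size) gives the numbers: "We will enroll 86 PD participants (43 individuals with PD and normal cognition and 43 individuals with PD mild cognitive impairment"), and "Data from 43 age/education/sex matched HA will be sampled from an extant repository". It sizes the accuracy analysis by interval width: "a sample of 129 participants will detect sensitivity and specificity values of 0.83 or higher with a 90% confidence interval precision of 0.10". That calculation takes the share of people with PD-MCI to be 30%. It attaches no error rate to the 80% mark.

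The documents do not state the number of candidate models, how one of them becomes the deciding model, the cut-off or assignment rule, or whether specificity is counted among PDN alone or among PDN and HA together.

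**The concern.** The measures used to compare the candidate models are the measures on which the endpoint is judged. If the analyst may look at several models, each at many thresholds, and report the one that clears 80% on both, the endpoint becomes a maximum over many correlated attempts. A function whose true accuracy is below the mark then has several chances to appear above it, and the operating point reported with it is optimistic.

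This is distinct from scoring a model on the data that fitted it. If every model were cross-validated and the model or cut-off were then chosen by its cross-validated accuracy, the choice itself would still push the reported figure up.

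What is at stake is the study's only stated primary endpoint, and the sensitivity and specificity that later work would take from it.

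**Working it through.** **The plan's own figure.** The required total is N = z² p(1 − p) / d² / prevalence. With z = 1.645 (90% interval), p = 0.83, d = 0.10 as half-width and prevalence 0.30, this gives 1.645² × 0.83 × 0.17 / 0.01 = 38.2 cases, and 38.2 / 0.30 = 127.3. That is close to the stated 129, so the sample-size statement reproduces. It is a precision calculation for one estimate from one classification and makes no allowance for choosing among several.

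**Inputs for the check.**
- From the documents: 43 PD-MCI, 43 PDN, 43 HA, and a pass mark above 80% on both measures.
- From arithmetic: 34/43 = 79.1% fails and 35/43 = 81.4% passes, so a pass needs at least 35 of 43 in each group.
- Assumed, not in the documents: PD-MCI against PDN; normal scores with equal variance; scores taken as given (no fitting optimism); true sensitivity = specificity = p, with p from 0.70 to 0.80; 3 to 6 equally good candidate models with score correlation 0.9.

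**One model, cut-off fixed in advance.** P(pass) = P(Bin(43, p) ≥ 35)². At p = 0.75 this is 0.2175² = 4.7%.

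**Any cut-off.** Scores are simulated with group separation 2z(p). A model passes if the 35th largest PD-MCI score exceeds the 35th smallest PDN score, because some threshold then clears both marks. With several models, the study passes if any of them does.

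| True p | Fixed cut-off | One model, any cut-off | Ratio to fixed | Best of 3-6 models, any cut-off (correlation 0.9) | Ratio to fixed |
|---|---|---|---|---|---|
| 0.70 | 0.45% | 1.8% | 4.0 | 3.6-5.7% | 8-13 |
| 0.75 | 4.7% | 13.1% | 2.8 | 24.4-32.0% | 5.2-6.8 |
| 0.78 | 14.0% | 31.9% | 2.3 | 50.5-60.7% | 3.6-4.3 |
| 0.80 | 25.0% | 49.4% | 2.0 | 68.9-77.6% | 2.8-3.1 |

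**Sensitivity of these results, at p = 0.75.**
- Sample-midpoint boundary, which is what a discriminant analysis would normally use: about 6%. Cut-off choice then multiplies by about 13.1 / 6.1 = 2.1.
- Lower score correlation gives more inflation: six models at correlation 0.7 give 40.2%, or 40.2 / 4.7 = 8.6-fold.
- PD-MCI against 86 PDN plus HA (pass at 69/86 for specificity): 3.5% fixed, 11% at any cut-off, 21-28% for 3-6 models at correlation 0.9.
- Eight variables scored on their own fitting data: 16.7% at the sample midpoint and 30.3% at any cut-off, so a single model without resampling is already well above 4.7%.
- Leave-one-out scores (800 simulations, eight variables): 2.1% for the eight-variable function at a fixed cut-off, 5.4% at any cut-off, and 19.8% for the best model in the stepwise sequence at any cut-off. Variable selection was not repeated inside the leave-one-out, so part of the last figure comes from that.

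**The case against.** The strongest reply is that Aim 2 does contain a selection rule: stepwise Wilks' lambda leads to a final variable set, and the ROC curves are there to describe accuracy, not to supply a cut-off. The study is observational and is sized for interval width, not for a pass/fail test, so a false-pass rate may look like the wrong yardstick.

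Part of this stands. A reader might infer that the plan declares success if any model at any cut-off exceeds 80%. The documents do not say so; they leave it open. A reader might also infer that the endpoint decides whether the function moves to a next phase. No section says that either.

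The reply does not close the gap. The Wilks' lambda step has no stated criteria, and the same paragraph then expects more than one model and compares them on the endpoint's own measures. Even a single final model would lack a cut-off and a named comparison. However the sample was sized, section 1.0 does set a numeric mark, and nothing separates the descriptive ROC work from the judgement against it.

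It is also tempting to state a single multiple, such as a tripling from cut-off choice. The documents do not support one: true accuracy, the number of models and their correlation are all assumed, and the multiple changes with each.

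**Conclusion.** The omission is real and the direction of the bias is clear: the plan as written permits a selected result to be reported as though it were the only one examined. Over true values of 0.70 to 0.80, with 43 against 43 and fitting optimism excluded, the chance of a false pass relative to a cut-off fixed in advance rises about 2- to 4-fold from cut-off choice alone, and about 3- to 13-fold with 3-6 models at correlation 0.9. Against the sample-midpoint boundary, cut-off choice at 0.75 gives only about 2-fold. These are conditional illustrations, not properties of the trial. This should be corrected before analysis; it does not call the design or the data collection into question.

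**What to change.** Before the data are analysed, state in Aim 2 and in the endpoint definition:

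1. One comparison for the endpoint, for example PD-MCI against PDN.
2. One function: either the final function from the stepwise Wilks' lambda rule, with entry and removal criteria given, or the full eight-variable function.
3. One classification rule valid for that comparison, not a point picked from the ROC curve. If PD-MCI and PDN are analysed as two groups, use the equal-prior two-group boundary. If the three-group function is used, assign each person to the group with the largest posterior probability. A posterior cut of 0.5 should not be carried over to three groups. In simulations with pairwise accuracy 0.85, it gave PD-MCI sensitivity of about 0.72 against 0.76 for largest posterior when the groups are equidistant, and 0.76 against 0.85 when PDN and HA coincide.

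Judge both measures against 80% from cross-validated or bootstrap-corrected estimates, with variable selection and any data-chosen model or cut-off repeated inside each resample. Label all other models and thresholds exploratory, and report AUC as a secondary measure.

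The cost is some analysis-plan wording and the resampling code, with no new participants or data. The downside is that a good function passes less often. At true sensitivity and specificity of 0.85, with scores taken as given, the pass rate falls from about 89% (one model, any cut-off) to about 66% (cut-off fixed in advance) or 73% (sample midpoint).
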